Annex 1: Patient questionnaire

	Strongly disagree (1)	Disagree (2)	Neutral (3)	Agree (4)	Strongly agree (5)
I experienced fewer side effects with Multigam 10%					
I experienced time gain with Multigam 10%					
I will therefore have a more productive day					
For my own situation I am in favor of using Multigam 10%					

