Primary objective	Assess the administration of Multigam 10% compared to Multigam 5% to shorten the infusion time without additional side effects and loss of quality of care.
Secondary objectives	
 • Evaluate the tolerability and infusion related side effects. • Evaluate patient satisfaction. • Evaluate the number of care actions required. • Evaluate nursing staff satisfaction.
Setup	
In this non-interventional, monocentric, observational study, the administration of Multigam 10% will be compared with the standard (Multigam 5%) in patients with a secondary immunodeficiency due to a hematological disorder.
 
Patients who are being treated with Multigam because of

	
their secondary immunodeficiency will be evaluated for inclusion.
 
The last administration of Multigam 5% will serve as a control. During this check, different parameters will be evaluated:
 
 -Infusion time (hours) -Hospitalization time at the oncological day clinic (hours) -Side effects (via CTCAE v4.03) -Nursing staff care actions 
Subsequently, an identical evaluation will take place at the first administration of Multigam 10% and the satisfaction of the patient and the nursing staff will also be assessed. The results will be analyzed and compared.
 
Patients can then receive Multigam 10% or Multigam 5% according to their preference.
  <pre> graph TD A[Screening] --> B["Multigam 5% administration"] B --> C["First evaluation"] C --> D["Multigam 10% administration"] D --> E["Final evaluation"] </pre>
Endpoints	
Primary:
 
To compare the infusion time (hours) and tolerance of Multigam 10% and the standard administration of Multigam 5%.

	
Secondary:
 
 • Assess the tolerance and patient satisfaction of Multigam 5% vs. Multigam 10% via: 
 - Patient questionnaire - Scoring of side effects via CTCAE v4.03 • Assess nursing staff care actions • Assess the satisfaction of the nursing staff (questionnaire) • Patient characterization (age, gender, disorder)
Population	30 patients with a secondary immunodeficiency due to a hematological disorder.

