Inclusion criteria	
 • Age \geq 18 years • Secondary immunodeficiency due to a hematological disorder • Patient received at least 2x Multigam 5% • No side effects (grade 2 or higher according to CTCAE v4.03) during their last 2 Multigam 5% infusions • Patient needs at least 2x Multigam • Signed informed consent form
Exclusion criteria	
 • Patient received less than 2x Multigam 5% • Side effects (grade 2 or higher according to CTCAE v4.03) during their last 2 Multigam 5% infusions • Patient refuses to participate in the study
Maximum duration of study/treatment	
 • 2 months
Version and date of final protocol	Version 3 – 8 September 2017

2. Background and rationale

Background

The immune system ensures the detection and elimination of pathogens and even transformed cells. However, normal functioning can be disrupted by a variety of factors. Both primary and secondary causes can lead to an immune deficiency with increased vulnerability for infections (Cooper, et al. 2003, Shinen & Shearer, 2008).

Secondary immune deficiencies can be caused by various diseases (lymphoproliferative disorders, infections, ...) and therapies (immunosuppressants, anti-inflammatory drugs, ...). In lymphoproliferative disorders such as chronic lymphocytic leukemia (CLL) and multiple myeloma (MM), both treatment and the disease itself contribute to a secondary immunodeficiency. In order to strengthen the resistance in these patients, substitution therapy with immunoglobulins can be started in cases of recurrent infections (Friman, et al. 2016). Intravenous gamma globulins (IVIg) are reimbursed in Belgium for patients with CLL and MM with a secondary immunodeficiency that resulted in a life-threatening infection or in repeated episodes of clinically significant infections requiring antibiotics. The dose is 0.4 to 0.5 g / kg every 3 to 4 weeks.

At the UZ Leuven Hematology department, Multigam is being used as standard IVIg substitution therapy. Multigam is an immunoglobulin preparation that is produced from the plasma of human donors. It exists in both 5% and 10% concentrated solution and is administered intravenously.

Rationale

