4.1 Inclusion criteria

- Age \geq 18 years
- Secondary immunodeficiency due to a hematological disorder
- Patient received at least 2x Multigam 5%
- No side effects during their last 2 Multigam 5% infusions
- Patient needs at least 2x Multigam
- Signed informed consent form

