4.3 Expected duration of study

- Start-up: february 2017
- Recruitment: 4 weeks
- First participant: Q2 2017
- EC submission: Q2 2017
- Final reporting: december 2017

5. Study actions per visit

5.1 Study visit 1

- Sign information and consent form
- Multigam 5% administration
- Questionnaire concerning IVIg administration
- CTCAE v4.03 scoring during and after infusion

5.2 Study visit 2

- Multigam 10% administration
- Questionnaire concerning IVIg administration
- CTCAE v4.03 scoring during and after infusion
- Patient questionnaire
- Nursing staff questionnaire

6. Data collection

The following data will be stored in the eCRF:

- Patient characteristics (age, gender and disorder)
- Infusion time (hours)
- Hospitalization time at the oncology day center (hours)
- Safety reporting (collect AEs en SA's according to CTCAE v4.03 criteria)
- Questionnaire concerning IVIg administration (both visits, annex 2)
- Patient satisfaction questionnaire (last visit; annex 1)
- Nursing staff satisfaction questionnaire (last visit; annex 3)

7. Assessment of efficiency

Primary endpoint:

- **Comparing the infusion time and tolerance**

Evaluate via time measurements, questioning and AE reporting during both treatments

Secondary endpoints:

- **Satisfaction and therapeutic tolerance**
 - Evaluation of satisfaction via questionnaire and tolerance via AE reporting
- **Safety**
 - Evaluate AEs and SAEs via CTCAE v4.03 criteria
- **Care actions**
 - Evaluate the number of nursing actions per patient
- **Satisfaction of nursing staff**
 - Evaluation of satisfaction via questionnaire
- **Patient characterization**
 - Characterization of patients (age, gender, disorder)

8. Assessment of safety

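### Disagreement with the only side-effect item in Annex 1 does not separate unchanged from worse; a fewer/same/more question would (minor)

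*Combined protocol and SAP*

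**What the plan says.** Annex 1 has four statements rated from 1 (strongly disagree) to 5 (strongly agree). Only the first concerns side effects: "I experienced fewer side effects with Multigam 10". The form is completed at visit 2 only (flowchart in 3.6; section 5.2), and section 6 describes it as "Patient satisfaction questionnaire (last visit; annex 1". No section defines what the middle or lower boxes mean for this item.

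The documents describe the form's role in two ways. The synopsis introduces the patient questionnaire and CTCAE scoring together under "Assess the tolerance and patient satisfaction of Multigam 5% vs. Multigam 10% via", and section 3.3 groups them similarly. Section 7 separates them: "Evaluation of satisfaction via questionnaire and tolerance via AE reporting". Sections 5.1 and 5.2 both schedule "CTCAE v4.03 scoring during and after infusion". Section 9.2 plans descriptive statistics for satisfaction and names no analysis of the CTCAE data.

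Two further passages bear on how patients can answer. The synopsis states that "The last administration of Multigam 5% will serve as a control", but the item does not name a reference infusion. On entry, the synopsis requires "No side effects (grade 2 or higher according to CTCAE v4.03) during their last 2 Multigam 5% infusions", whereas section 4.1 requires "No side effects during their last 2 Multigam 5% infusions", with no grade limit.

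**The concern.** The primary objective is a shorter infusion without added side effects. The useful patient answer is therefore whether side effects were more or not more, and the item asks only about fewer. Disagreement is literally true both for a patient with no change and for a patient who got worse.

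Eligibility adds to this. Patients enter with no side effects, or with grade 1 at most, in their last two 5% infusions. That leaves little room for improvement, so many truthful answers may fall in the part of the scale that cannot be interpreted. A well-tolerated 10% product could even look unfavourable, because unchanged patients may disagree.

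What is at stake is a descriptive, patient-reported result. Because the synopsis lists the questionnaire beside CTCAE under tolerance, the item could be quoted as tolerance evidence in either direction.

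**Working it through.** The only stated figure involved is the sample of 30 (section 9.1). It cannot be reproduced, because no error rate, power, effect size, standard deviation or event rate is given. It is taken as it stands; the point does not depend on how it was chosen.

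**Inputs from the documents:** n = 30 (9.1); scale 1 to 5 (Annex 1); one administration, at visit 2 (3.6, 5.2, 6).

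**Assumptions:** better patients tick 4 or 5; unchanged patients tick 1, 2 or 3; worse patients tick 1 or 2. The numbers better and worse below are illustrations, not estimates.

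**Step 1: range of disagreement.** Let B, S and W be the numbers better, same and worse, with B + S + W = 30, and let D be the number ticking 1 or 2. D is smallest when every unchanged patient ticks Neutral and largest when every unchanged patient disagrees, so W ≤ D ≤ S + W = 30 − B.

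| W | D if B = 0 | D if B = 3 |
|---|---|---|
| 0 | 0–30 | 0–27 |
| 3 | 3–30 | 3–27 |
| 6 | 6–30 | 6–27 |

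**Step 2: reading the result back (B = 0).** Since W cannot exceed D:

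- D from 0 to 2 excludes 3 or more worse.
- D from 3 to 5 excludes 6 worse but fits 0 or 3.
- D from 6 to 30 fits 0, 3 or 6 worse.

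**Step 3: the mean score is no clearer (B = 0).** The minimum is 1.0 in every case. The maximum is (3S + 2W)/30:

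- W = 0: 90/30 = 3.0
- W = 3: (81 + 6)/30 = 2.9
- W = 6: (72 + 12)/30 = 2.8
- W = 30: 60/30 = 2.0

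A mean between 1.0 and 2.0 therefore fits anything from all unchanged to all worse.

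**Step 4: relaxing the response assumption.** If a worse patient may also tick Neutral, the upper limit on W becomes the number not agreeing. With 10 not agreeing, the share worse is 0 to 10/30 = 33%; with 20 not agreeing, 0 to 20/30 = 67%. Absence of disagreement would then no longer exclude worsening.

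**Step 5: what a direct question would give.** For x of 30 answering more or many more, the exact (Clopper-Pearson) 95% limits are the 0.025 quantile of Beta(x, 31 − x) and the 0.975 quantile of Beta(x + 1, 30 − x), with lower limit 0 when x = 0:

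- 0/30 = 0% (0 to 11.6%)
- 3/30 = 10% (2.1 to 26.5%)
- 6/30 = 20% (7.7 to 38.6%)

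The intervals are wide at this sample size, but they estimate the quantity of interest directly.

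**The case against.** The strongest reply is that tolerance is measured elsewhere. CTCAE v4.03 is scored at both visits, all adverse events are collected from consent to the last visit (8.2.1.5), and section 7 gives the questionnaire satisfaction and adverse event reporting tolerance. Section 7 does list questioning among the means for the primary endpoint, but it does not name Annex 1, and 9.2 plans no inference from item 1. This stands. A reader might infer that the study cannot detect worse tolerance; the documents do not support that.

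A second reply is that the ranges in the working are worst cases for the item read alone. Answers and adverse events are both held in the eCRF, so each patient's answer can be set beside that patient's grades. This also stands: linking narrows the ranges, although without data no narrower range can be given.

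A third reply is that patients will use Neutral for no change. Some may, but nothing on the form tells them to, so the lower boxes remain open to both meanings. A descriptive summary still depends on categories with one meaning.

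**Conclusion.** The point holds as a minor, inexpensive improvement. When patients disagree with item 1, the answer does not tell unchanged from worse. In the illustration, any count of 6 or more disagreeing out of 30 is compatible with 0, 3 or 6 patients worse. This assumes that worse patients tick only the two disagree boxes, that unchanged patients may tick any of the lower three, that nobody is better, and that the item is read alone.

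Two stronger readings are tempting and should be resisted.

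- A reader might infer that the item can never support an absence of worsening. Under the same response assumptions, no disagreement means nobody worse, so low disagreement is informative.
- A reader might infer from section 4.1 that no patient could have fewer side effects on 10%. Section 5.1 places consent and a 5% infusion at visit 1. If that infusion follows the two qualifying ones, side effects could occur there and improvement is possible. The documents do not settle this.

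The entry criteria in the synopsis and in section 4.1 differ on grade and must be reconciled. How they are reconciled affects how much room there is for improvement, not whether the item is ambiguous.

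**What to change.** 1. Replace item 1 with a separately formatted question: *Compared with my last Multigam 5% infusion, my side effects with Multigam 10% were: many fewer / fewer / the same / more / many more.* This also names the reference infusion, in line with the control defined in the synopsis.
2. In 9.2, report the full distribution and the share answering more or many more with an exact 95% confidence interval, beside the same patients' CTCAE grades.
3. For forms already completed, report the old item separately, beside each patient's CTCAE grades, and do not read disagreement as either no change or worsening.

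**Cost.** The changed form needs ethics review within a short planned timeline (4 weeks of recruitment, final reporting in December 2017). The question will have a different response scale from the other three items. There may be two item versions among about 30 patients: protocol version 3 is dated 8 September 2017, after the planned first participant in Q2 2017, and the documents do not show whether forms had been completed by then. No extra visit or patient is needed.

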Annex 2: Questionnaire concerning IVIg administration (to be filled in by nursing staff)

	Multigam 5%
Infusion time (..hour..minutes)	Start: h min Stop: h min
Number of care actions	
	Multigam 10%
Infusion time (..hour..minutes)	Start: h min Stop: h min
Number of care actions	

Care action means both the increase or decrease of infusion rate and any other intervention due to intolerance / complication.

Annex 3: Nursing staff questionnaire

	Strongly disagree (1)	Disagree (2)	Neutral (3)	Agree (4)	Strongly agree (5)
I have been able to plan patients more efficiently with Multigam 10%					
I have experienced time gain with Multigam 10%					
I am in favor of using Multigam 10%
